Scheduled unsedated colonoscopy was adopted at West LA VAMC to manage inefficiency of cancellations due to lack of escorts. Veterans without escorts were offered the option (Table 3).

Table 3. The scheduled unsedated option was formally adopted on 6/3/2013, at a meeting	with all the
schedulers when the comparison of sedated and unsedated colonoscopy was discussed (15).	

		7 C C C C C C C C C C C C C C C C C C C
Attributes of scheduled options	Sedated	Unsedated
Availability; cecal intubation rate	Standard in U.S.; ~90%	Not usual in U.S.; 80-90%
Sedation risks: hypotension, hypoxia, arrhythmia, etc.	Very small	No
Need to consume purge preparation; escort requirement	Yes; Mandatory	Yes; Not required
Drive after colonoscopy; discomfort reduced by medication	No; likely	Yes; not applicable

Excluding poor preparation and obstruction, cecal intubation was 94.6% and failure due to pain was 5.4% (Table 4). Colonoscopists were willing to perform and supervise unsedated colonoscopy. The option effectively managed last-minute cancellations by patients (3% were female Veterans) without escorts (15).

Table 4. Number of unsedated colonoscopies, no shows, and acceptance by colonoscopists. [*Fisher's exact test.]						
Date	1/1/13-6/10/13	6/11/13-11/22/13	р			
Unsedated colonoscopies	30/1073 (2.8%)	126/1203 (10.5%)	0.0001*			
No shows due to lack of escorts	50/1073 (4.7%)	5/1203 (0.42%)	0.0001*			
Endoscopist participation in unsedated colonoscopy	8/22 (36%)	16/21 (76%)	0.0104*			

3. Sacramento VAMC (Participant - [name] and others)

Consecutive *male* Veterans who requested scheduled unsedated colonoscopy were randomized to WE (n=50) vs. air (n=50). 90% had no escort. WE showed lower [mean (SD)] RTMIP: 3 (3) vs. 5 (3) (p=0.0008); higher willingness to repeat: 76% vs. 48% (p<0.0007); numerically higher overall (54% vs. 48%), proximal (40% vs. 28%) and proximal <10 mm (36% vs. 28%) ADR; comparable cecal intubation rate 98% vs. 88%, and insertion times 13 (7) min vs. 12 (7) min (6).

(b) Coaching in WE by PI (Participants - [name], [name], Cohen, [name], [name] and others)

With experienced colonoscopists, impact of coaching (by PI) was established (my biosketch) (42).

(c) WECAC, WE, RTMIP & ADR (Participant - PD/PI, [name], [name], [name])

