Five colonoscopists with experience in WE performed WECAC at 3 sites (47) (Table 5, A). In 45 male patients completing without sedation, the low mean RTMIP of WECAC observed in a published pilot study (11) was reproduced (Table 5, A vs. B). In U.S. cohorts, mean RTMIP of WECAC was lower than those of historical unsedated cohorts examined by WE (5,6) (Table 5, A vs. C-D, respectively).

	Table 5: Comparison of real-time maximum insertion pain (RTMIP)						
Technique I		References	Study Sites	No. of Investigators (type of no sedation)	RTMIP		
Α	A WECAC 47		2 U.S., 1 Taiwan	5 (mixed on demand & scheduled unsedated)	1.5 (1.8)		
B WECAC		11	1 U.S.	3 (Scheduled unsedated)	1.2 (1.5)		
С	WE	5	1 U.S.	1 (Scheduled unsedated)	3.6 (2.1)*		
D	WE	6	1 U.S.	2 (Scheduled unsedated)	3 (3.0)*		

Frequency; mean (SD). A=unpublished preliminary; B=published pilot; RTMIP, real-time maximum insertion pain; VAS: 0=none, 10=most severe., *p < 0.05, vs. 1.5 (1.8), t test.

Table 6 shows comparable intubation rates. Trends favored WECAC in intubation time WECAC (18-20 min) vs. WE (13-34 min), right colon preparation WECAC (3.1-3.3) vs. WE (2.3-3.0), painless insertion WECAC (41-51%) vs. WE (10-28%); overall ADR (56% vs. 46%), and proximal colon ADR (46% vs. 40%).

	Table 6: Demographics and procedural outcomes										
Tec	hnique	n	Age (yrs)	BMI	PAS	PAS Cecal Intubation		Proximal Bowel	Painless	Overall ADR	Proximal
100	imique	''	Age (yrs)	DIVII	Yes Time Rate (%)		Prep Score	insertion	Overall ADIC	Colon ADR	
Α	WECAC	45	62 (10)	29 (4)	34%	20 (14)	96	3.1 (0.5)	51%	Combined	Combined
В	WECAC	26	64 (8)	31 (5)	1	18 (12)	96	3.3 (0.5)	41%	40/72 (56%)	33/72 (46%)
С	WE	42	66 (9)	32 (7)	1	34 (3)	97.6	3.0 (0.7)	10%	Combined	Combined
D	WE	50	61 (7)	30 (7)	30%	13 (7)	96	2.3 (0.5)	28%	42/92 (46%)	37/92 (40%)
DΛG	nrior and	omina	l curgary	Rowel	nran co	ore: 1-e	vcallant: 3	2- annd: 2- fair: 1	- noor Da	ta maan (SD)	· % total

PAS, prior abdominal surgery. Bowel prep score: 4=excellent; 3= good; 2= fair; 1= poor. Data, mean (SD); % total.

	Table 7: Procedural details					
Technique	Screening/	Position Change (%)	Abdominal	Water Volume on	Withdrawal	
recillique	Surveillance/	Position Change (70)	Compression (%)	Arrival to Cecum (L)	Time (min)	

		Diagnostic	Yes	Combined	Yes	Combined	Infused	Suctioned	
Α	WECAC	19/15/11	29	25%	44		1.6 (0.8)	1.9 (1.4)	21 (11)
В	WECAC	17/10/0	19	25%	30		1.3 (1.2)	1.4 (1.6)	23 (13)
С	WE	17/17/8	64	34%	57	400/	1.8 (0.7)		22 (13)

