Updated male Veteran sample size. Pilot data in scheduled unsedated male Veterans were updated. The real time maximum insertion pain (RTMIP) [mean (SD)] was 2.7 (2.2) with WE (n=87) and 1.5 (2.1) with WECAC (n=38). The reduction (44%) 2.7-1.5=1.2 is 1.2/2.2=0.55 standard deviation (SD) units. The sample size/group needed to detect a difference at a level of significance of 0.0492 (adjusted for Obrien-Fleming interim stopping rules, one interim analysis at 50% completion) with 90% power is 72 or 144 total using a twosided two sample t-test. Assuming 90% of subjects will be evaluable, we plan to recruit 160 male Veterans. Updated pilot data showed the PI performed 30 scheduled unsedated colonoscopies (male) in 1 year when ~2200 colonoscopies were offered at VAGLAHS (1.36%). At participating sites, a total of ~9000 colonoscopies (VAGLAHS 2200, VANCHCS 3300, VAPAHCS 3500) will be performed each year. For purpose of conservative estimation, 1/2 of 1.36% (0.68%) of all colonoscopies will be presumed to be in scheduled unsedated male Veterans when the option is made available up front. In 51 month (4.25 year) enrollment period, a total of 38250 colonoscopies will be performed. 260 (0.68% of 38250) male Veterans will receive scheduled unsedated colonoscopy, making target enrollment of 160 achievable (only 160/260 = 62% enrollment rate needed). In support of this possibility, in two prior RCT in scheduled unsedated male Veterans at VAGLAHS and VANCHCS comparing WE vs. air colonoscopy, high enrollment rates of 97.7% (84/86) and 95.2% (100/105), respectively, were recorded. Sample size of 160 will be sufficient to show significant differences in some of the previously listed secondary outcomes related to quality colonoscopy in

Secondary outcome power estimates based pilot data in WE (n=87) and WECAC (n=38) in male Veterans					
Secondary Outcomes	Pilot (WE vs. WECAC)	Difference (SDU or %)	Sample size per group needed*		
Recalled pain, score (SD)	1.5(2) vs. 0.5(2)	1 (0.5 SDU)	84 (Will be dropped)		
Successful cecal Intubation	98% vs. 100%	2%	(Will be dropped)		
Proportion with no pain	18% vs. 46%	28%	54		
Insertion time, minutes (SD)	15(5) vs. 12( 5)	-3 (0.6 SDU)	58		
Overall ADR - entire colon	36% vs. 50%	14%	258		
Proximal colon ADR	17% vs. 40%	23%	76		
Right colon ADR	20% vs. 40%	20%	106		
Willing to repeat, score (SD)	9.0(2.5) vs. 9.6(0.9)	0.6 (0.4 SDU)	(Will be dropped)		

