ADR, adenoma detection rate; SD, standard deviation; U, units. *90% power, 95% confidence or 5% α error level.					

male Veterans (e.g. proportion with no pain, insertion time, proximal colon ADR). The remaining previously listed secondary outcomes in male Veterans will be dropped (e.g. recalled pain, successful cecal intubation, overall and right colon ADR, willing to repeat).

Updated female Veteran sample size. After receipt of the critique, the PI identified 9 scheduled unsedated female Veterans (5 WE, 4 WECAC). RTMIP were WE, 6.2 (3.5) and WECAC, 3.5 (3.7). The reduction (44%) was 2.7/3.7 or 0.7 SD unit. The female Veterans had significantly higher RTMIP than the male Veterans when examined by WE, but the percent reduction of RTMIP by WECAC was equivalent (44%). The sample size/group needed to detect a difference at a level of significance of 0.0492 (adjusted for Obrien-Fleming interim stopping rules, one interim analysis at 50% completion) with 90% power is 43 or 86 total using a two-sided two sample t-test. Assuming 90% of subjects will be evaluable, we plan to recruit 96 female Veterans. Sample size of 96 will be sufficient to show significance in differences in some of the previously listed secondary outcomes related to quality colonoscopy in female Veterans (e.g. proportion with no pain, insertion time, overall and segmental ADR). The remaining previously listed secondary outcomes in female Veterans will be dropped (e.g. recalled pain, successful cecal intubation, willing to repeat).

Secondary outcome power estimates based pilot data in WE (n=5) and WECAC (n=4) in female Veterans					
Secondary Outcomes	Pilot (WE vs. WECAC)	Difference (SDU or %)	Sample size per group needed*		
Recalled pain, score (SD)	3.1(3) vs. 1.6(3)	1.5 (0.5 SDU)	84 (Will be dropped)		
Successful cecal Intubation	100% vs. 100%	0%	(Will be dropped)		
Proportion with no pain	0% vs. 25%	25%	32		
Insertion time, minutes (SD)	17(4.5) vs. 14(4.5)	-3 (0.7 SDU)	43		
Overall ADR - entire colon	20% vs. 50%	30%	48		
Proximal colon ADR	20% vs. 50%	30%	48		
Right colon ADR	20% vs. 50%	30%	48		
Willing to repeat, score (SD)	9.2(1.1) vs. 9.5(1.0)	0.3 (0.3 SDU)	233 (Will be dropped)		
ADR, adenoma detection rate; SD, standard deviation; U, units. *90% power, 95% confidence or 5% $\alpha$ error level.					

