Primary hypothesis. Real-time maximum insertion pain (RTMIP) is significantly lower in the patients examined by the WECAC technique compared with the WE technique. The analysis will compare 2 groups (WECAC vs. WE) with a two sample t-test. If the data show substantial non-normality (as in a prior dataset with WE (5)); we will compare the groups with a Mann-Whitney *U* test; P<0.0492 considered significant. Secondary analysis of the primary outcome will utilize mixed effects regression models to evaluate the effects of potential covariates/confounds described in Tables 9 and 10. First, we will assess the effect of each individual covariate in regression models including the effect for group assignment and gender (stratification factor in the randomization), as well as the covariate by group interaction. Next, we will construct a multiple regression model with the set of covariates found to be significant (either as a main effect or an interaction effect) in an overall regression model along with group assignment.

Dependent Variables	Variable Type	Analysis method
Primary Outcome		
RTMIP (0=none,	Continuous	2 sample Student t test. However, if distribution of the data is skewed as
10=most severe)	Continuous	seen in an earlier study (5), the Mann-Whitney U test will be used.

We have updated the analytic plan to include multi-level random effects (hierarchical model) for study site and provider within site. We will include two levels of random effects in this model: 1. random effects for study site, 2. random effects for provider which will be nested within sites.

Secondary hypotheses. WECAC produces significantly higher quality colonoscopy outcomes. For example, when WE alone and WECAC are compared, the proportion completing colonoscopy with no pain, insertion time, and ADR in the proximal colon will be significantly different. For continuous secondary outcomes (e.g. insertion time), we will use a similar analysis strategy as that used for the primary outcome. For dichotomous secondary outcomes (e.g., no pain, proximal colon ADR) we will use Chi-square tests to compare the outcomes between the groups. Generalized logistic models will be used to adjust for covariates, gender and study site for these outcomes.

Dependent Variables	Variable Type	Analysis method
Insertion time	Continuous	Student t test
No insertion pain (yes, no); proximal colon adenoma detection (yes, no)	Binary	Chi square

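### The 17% WE proximal ADR behind the claim that 160 men suffice conflicts with the SAP's own table and with the protocol's WE cohorts

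*SAP*

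**What the plan says.** Under Updated male Veteran sample size, the SAP sets enrolment from RTMIP ("with 90% power is 72 or 144 total") and plans 160 men on the assumption that 90% will be evaluable. It then adds: "Sample size of 160 will be sufficient to show significant differences in some of the previously listed secondary outcomes related to quality colonoscopy in" "male Veterans (e.g. proportion with no pain, insertion time, proximal colon ADR").

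The support is the table headed "Secondary outcome power estimates based pilot data in WE (n=87) and WECAC (n=38) in male Veterans", with a footnote specifying "90% power, 95% confidence". Two rows matter here:

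- Proximal colon ADR: 17% (WE) vs 40% (WECAC), 76 per group, kept.
- Right colon ADR: 20% vs 40%, 106 per group, dropped.

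The protocol defines the proximal colon as cecum to splenic flexure (secondary outcome measures) and the right colon as cecum to hepatic flexure (Table 10).

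The protocol also reports WE results from earlier cohorts. For the Sacramento RCT of WE against air it reports "numerically higher overall (54% vs. 48%), proximal (40% vs. 28"%). For Table 6, with WECAC given first, it reports "overall ADR (56% vs. 46%), and proximal colon ADR (46% vs. 40"%), from 33/72 and 37/92 patients. The SAP places the two earlier RCTs of WE against air, both in scheduled unsedated male Veterans, at VAGLAHS and VANCHCS.

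**The concern.** The sufficiency claim for proximal ADR depends on the 17% control rate, and two things in the documents speak against it. First, a region cannot have a lower detection rate than a part of itself in the same patients, yet the table gives 17% for the proximal colon and 20% for the right colon. Second, the same technique in the same kind of patient, at two of the three trial systems, gave 40%. The sizing rate lies below even the 28% of Sacramento's air arm. No text explains the difference.

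Proximal ADR is one of three named secondary outcomes, and specific objective (b) makes preparation of a cooperative study conditional on an increase in it. If the stated power is too high, a non-significant result in men would look more informative than it is.

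**Working it through.** **Inputs.** Two-sided α = 0.05 (the table does not state sidedness), 90% power, 1:1 allocation, chi-square test ("we will use Chi-square tests to compare the outcomes between the groups"). Per arm: 160/2 = 80 randomized; 0.9 × 80 = 72 evaluable. The SAP's intention-to-treat rule supports 80, its evaluability assumption 72, so both are shown.

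**Formulas.** With V = p1(1−p1) + p2(1−p2) and d = |p1−p2|:

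- n per group = (1.960 + 1.2816)² × V/d² = 10.507 × V/d² (unpooled variance).
- Power = Φ(d/√(V/n) − 1.960), unpooled. The pooled form is Φ([d√n − 1.960√(2p̄(1−p̄))]/√V), where p̄ is the mean of p1 and p2. Ranges below run from pooled to unpooled.

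**The plan's figure.** 17% vs 40%: V = 0.1411 + 0.2400 = 0.3811, d² = 0.0529, n = 75.7, so 76. It matches. The same formula returns the table's other male binary rows (54, 106 and 258), so this is the method that was used. Power is 87-88% at 72 and 90-91% at 80.

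**Check inside the table.** 17% of 87 is about 15 men with a proximal adenoma; 20% of 87 is about 17 with a right colon adenoma. Every man in the second group belongs in the first. If both rows describe the same 87 men, the two figures cannot both be right, and with right colon ADR at 20% the proximal rate is at least 20%.

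**Check against the protocol.** Sacramento WE: 40% of 50 = 20. The rest of Table 6: 37 − 20 = 17 of 42, also 40%. A pilot with about 15 positive men cannot contain either whole arm. If 15/87 and 37/92 are independent, Fisher's exact p is about 0.001 (95% CI about 10-27% and 30-51%).

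**Power with other control rates.**

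| WE vs WECAC | Basis | n per group for 90% (unpooled / pooled) | Power at 72 | Power at 80 |
|---|---|---|---|---|
| 17% vs 40% | SAP row | 76 / 79 | 87-88% | 90-91% |
| 20% vs 40% | control raised to the right colon rate | 106 / 109 | 75-77% | 79-81% |
| 20% vs 43% | same, 23-point gain kept | 81 / 84 | 85-87% | 89-90% |
| 40% vs 63% | Table 6 control, 23-point gain kept | 94 / 98 | 79-81% | 84-85% |
| 40% vs 46% | Table 6, both rates | 1,426 / 1,429 | 11% | 12% |

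Example, second row at 72: V = 0.16 + 0.24 = 0.40; 0.20/√(0.40/72) = 2.683; 2.683 − 1.960 = 0.723; Φ = 0.765. In the last row the unrounded fractions 37/92 and 33/72 give about 10% and 11%, and about 1,630 per group.

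**The case against.** The best defence is that nothing was miscalculated. The 76 is correct for its inputs, and 80 per arm under intention-to-treat gives 90% power on those inputs. The sentence is also hedged: it speaks of some outcomes, by way of example, and it holds for no pain (54 per group) and insertion time (58). All of this stands. The fault is one input and one named example.

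A second defence is that the pilot may be the better contrast, since both its arms are scheduled unsedated male Veterans. Table 6's WECAC cohorts are not randomized against WE, and one includes a Taiwan site and on-demand unsedated patients. The segment definitions used in the earlier RCTs are not given either. This limits what can be made of the 46%, but it does not explain why WE gave 40% in two RCT arms, and it leaves the conflict inside the table untouched. That conflict shows that at least one of 17% and 20% is wrong, not by itself which; the 40% suggests that the proximal figure is too low.

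Third, the conclusion depends on the gain assumed. At 20% with the 23-point gain kept, 80 per arm falls only just short of 90%. Keeping the pilot odds ratio (3.25) from a 40% control would put WECAC at about 68% and need only 63 per group. No document reports such a WECAC rate.

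Stronger readings are tempting. A reader might infer that true power is about 10%; that treats a six-point gap between non-randomized cohorts as the effect. A reader might pool the pilot and Table 6 WECAC samples for a firmer rate; the documents do not exclude that they share patients. A reader might infer that the trial is too small; its size is set by RTMIP, which this point does not touch.

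**Conclusion.** The statement that 160 men suffice for proximal colon ADR is not supported as written. The 17% control rate cannot stand beside the 20% right colon rate in the same patients, and it is unreconciled with the 40% seen with WE at two of the three trial systems. Moving the control to 20% with WECAC left at 40% lowers power to about 75-77% at 72 per arm or 79-81% at 80, against the 90% claimed. From a 40% control, power is about 79-81% or 84-85% if the whole 23-point gain holds, and about 10-12% if the gain is only the six points of Table 6, which is indicative only.

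This assumes two-sided testing at 0.05, equal arms, and that the two ADR rows describe the same pilot patients. It does not show an arithmetic error, and it does not show that a null result is likely: the documents do not settle the true gain. The plan nowhere says that a non-significant ADR result would be read as no effect; the risk is that the stated power invites that reading.

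**What to change.** In the SAP, under Updated male Veteran sample size:

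1. Check the 17% against the pilot records, together with the 20% for right colon, and correct whichever row is wrong. Say how the result relates to the 37/92 in protocol Table 6.
2. Remove proximal colon ADR from the outcomes that 160 men are said to be sufficient for. Leave no pain and insertion time as they are.
3. State power for male proximal ADR at 72 and 80 per arm for WE rates from 20% to 40%, with the assumed gain shown beside each figure. Do not use a pooled WECAC rate unless overlap between the samples has been ruled out.
4. Commit to reporting the male difference in proximal ADR with a 95% CI, and state that a non-significant result will not be taken as evidence of no effect.

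The cost is a look at the pilot data and a few lines of SAP text. Enrolment, endpoints and tests do not change. The stated power for one secondary outcome becomes less favourable.

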Exclusion criteria. Decline to be randomized, unable to give consent or respond to questionnaires, history of colon surgery, active inflammatory bowel disease, lower gastrointestinal bleeding (except for occult blood or FIT positive in the context of colon cancer screening), therapeutic colonoscopy (e.g., hemostasis, removal of large polyp), proctosigmoidoscopy, bidirectional endoscopy, inadequate consumption of bowel preparation, known history of severe diverticulosis or diverticulitis, history of abdominal surgery previously requiring sedation for colonoscopy, current narcotic/anxiolytic medication use, prior unsuccessful experience with unsedated colonoscopy, emergent colonoscopy, evidence of colonic obstruction based on pre-colonoscopy clinical evaluation, current participation in other studies, medical condition that could increase the risk associated with colonoscopy (e.g., active cardiac or pulmonary disease or other serious disease), medical condition that would preclude a benefit from colonoscopic screening (e.g., cancer or any terminal illness), prosthetic heart valve, anticoagulant therapy, nonmedical problems (e.g., psychiatric disorders, excessive use of alcohol), need for special precautions in performing colonoscopy (e.g. antibiotic prophylaxis), and request of on demand sedation.

Primary outcome measure (for male and female subjects).

	_
Real time maximum insertion	_
pain (RTMIP) (unblinded) score	
(validation by correlation with	
recalled pain described below)	

Pain during insertion reported to the unblinded assisting nurse, visual analogue scale, VAS: 0=none, 10=most severe. The highest pain score will be tabulated for analysis. Timing of data collection will be at the discretion of the nurse to minimize bias by colonoscopist behavior.

Secondary outcome measures (for male and female subjects).

Proportion with no insertion pain Proportion report no pain during insertion of the colonoscope. Quality marker.

Insertion time	Time to cecum (clock display on monitor). Faster insertion is a quality marker
Proximal colon ADR	ADR from cecum to splenic flexure. Measure of high quality colonoscopy

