Primary outcome. Patient with insertion pain that cannot be brought to a tolerable level by colonoscopist implemented maneuvers will be considered failure of cecal intubation and the insertion will be discontinued. The pain level at the time of discontinuation will be noted for analysis.

Standardized validated instruments.

Proportion with no insertion pain, insertion time, proximal colon ADR (secondary outcomes in males) have been defined above; demographic data, co-morbidities, prior history and additional procedure based and patient level parameters will be analyzed as covariables (Tables 9 and 10).

Table 9: Demographic variables, co-morbidities and prior history				
Age	In years		Hemorrhoids	0=no, 1=yes
Gender	Male, female		Chronic pain treatments	0=no, 1=yes

Education	Elementary, high, college, graduate	Substance abuse	0=no, 1=yes
Ethnicity	White, Black, Hispanic, Asian, other	Prior abdominal surgery	0=no, 1=Yes (type)
BMI	Weight/height ²	Prior sedation colonoscopy	0=no, 1=yes
Indication	Screening, surveillance, diagnostic, pain	Prior unsedated colonoscopy	0=no, 1=yes

Table 10: Additional procedure based and patient level covariates				
Recalled maximum insertion pain	Maximum pain during insertion reported to a blinded observer after			
score (blinded data)	colonoscopy before discharge, VAS: 0=none, 10=most severe. Correlation with RTMIP.			
Overall ADR - entire colon	Proportion of patients with at least one adenoma of any size.			
Right colon ADR	ADR from cecum to hepatic flexure			
Adequacy of patient blinding	Patient guesses which method is used (<60% correct=adequate).			
Successful cecal intubation	0=no, 1=yes			
Successful cecal ilitubation	Abdominal pain prior to start of colonoscopy: 0, none to 3, severe (recorded			
Current abdominal discomfort	before examination)			
Loop reduction maneuvers	Number of times used, recorded by nurse assistant			
Position change	Start with left lateral, change as needed to supine, right lateral, prone.			
Abdominal compression	0=no, 1=Yes (sigmoid, transverse, hepatic, right side)			
Need to change technique	0=no, 1=yes (to air insufflation)			
Water volumes (insertion) Volume of water (infused and suctioned) upon arrival to the cecum, eq				
	volumes confirm appropriate application of water exchange			
Water volumes (total)	Volume of water (infused and suctioned) at the end of colonoscopy			
	Documented during withdrawal (4=excellent, no residual stool; 3=good, small			

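### The male secondary power table puts WE proximal colon ADR (17%) below WE right colon ADR (20%) in the same stated 87 men, which the protocol's segment definitions do not allow; one of the two inputs supports a sufficiency claim

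*SAP*

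**What the plan says.** In the SAP, under the updated male Veteran sample size, one table header covers every row: "Secondary outcome power estimates based pilot data in WE (n=87) and WECAC (n=38) in male Veterans". Two of its rows concern segmental ADR:

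| Row | WE | WECAC | Difference | Needed per group |
|---|---|---|---|---|
| Proximal colon ADR | 17% | 40% | 23% | 76 |
| Right colon ADR | 20% | 40% | 20% | 106 |

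The footnote sets 90% power and a 5% error level.

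The protocol defines the two segments. Its list of secondary outcome measures gives proximal colon ADR as "ADR from cecum to splenic flexure". Its Table 10 gives right colon ADR as "ADR from cecum to hepatic flexure". The overall ADR entry in Table 10 shows that ADR counts patients with at least one adenoma, not adenomas.

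The SAP then draws its conclusion for men: "Sample size of 160 will be sufficient to show significant differences in some of the previously listed secondary outcomes related to quality colonoscopy in" male Veterans, with the examples "proportion with no pain, insertion time, proximal colon ADR". Among the male outcomes to be dropped it lists "overall and right colon ADR, willing to repeat".

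**The concern.** Under these definitions every man with a right colon adenoma also has a proximal colon adenoma. In one group of men the proximal rate must therefore equal or exceed the right colon rate. The WE column shows the reverse.

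The row that is kept is the one with the lower WE rate. It supports the statement that 160 men suffice for proximal colon ADR, with 76 needed against 80 available per group. The right colon row, with the same WECAC rate and a WE rate three points higher, needs 106 per group, and that outcome is dropped. If the true WE proximal rate is at least the right colon figure, the retained outcome is in the same position as the dropped one.

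Proximal colon ADR is named in the protocol's secondary hypotheses, and an increase in it is the stated condition for preparing a multi-site cooperative study. Anyone reading a null male result would need to know whether the planned power was about 90% or about 80% or less.

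**Working it through.** **Inputs.** WE n=87, and the rates of 17%, 20% and 40%, come from the SAP male table. Power of 90% and a 5% error level come from its footnote. The footnote does not state sidedness; two-sided is assumed because it reproduces the table. The male target of 160 is split 1:1, so 160/2 = 80 per group.

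**1. Counts behind the WE percentages.** Out of 87:
- 14 = 16.1%, 15 = 17.2%, 16 = 18.4%
- 17 = 19.5%, 18 = 20.7%

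Only 15 rounds to 17%, and only 17 rounds to 20%. The table therefore implies 15 men with a proximal adenoma and 17 with a right colon adenoma. Rounding cannot close a gap of two men. With 15/87 proximal, a right colon rate that rounds to 20% would need a right colon denominator of 76 or fewer (15/76 = 19.7%). No such denominator is stated.

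**2. The plan's own sample sizes.** The unpooled two-proportion formula is

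n per group = (1.960 + 1.282)² × [p1(1−p1) + p2(1−p2)] / (p1−p2)², where (1.960 + 1.282)² ≈ 10.51.

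- 17% vs 40%: 10.51 × (0.1411 + 0.2400) / 0.0529 = 75.7, rounded up to 76. The table says 76.
- 20% vs 40%: 10.51 × (0.1600 + 0.2400) / 0.0400 = 105.1, rounded up to 106. The table says 106.

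The same formula gives the table's 54 (18% vs 46%) and 258 (36% vs 50%). The arithmetic is right; the conflict is between the inputs.

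**3. Power at 80 per group, WECAC held at 40%.** Two-sided 0.05:

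| WE proximal ADR | Exact power, chi-square test | Power by the table's formula | Needed per group for 90% |
|---|---|---|---|
| 17% | 91.0% | 91.5% | 76 |
| 20% | 80.1% | 80.7% | 106 |

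With WECAC fixed at 40%, a WE rate above 20% narrows the difference and lowers power further. About 80% is therefore the ceiling for any WE proximal rate of 20% or more.

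**4. Both sexes combined.** Total enrolment is 160 + 96 = 256, or 128 per group. If 20% vs 40% applied to everyone, 128 exceeds the 106 needed, and power is about 94% to 95% (exact and table formula).

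**The case against.** The strongest reply is that the effect is conditional. Right colon ADR is dropped for men. If 20% is the wrong entry, nothing the plan uses changes, and both 76 and the sufficiency statement stand. That is correct, and it is why the point is minor. It does not remove the contradiction, because only the pilot counts can show which entry is wrong.

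The pilot may also have coded its segments differently from the trial, or one row may have missing data. Either would reconcile the figures, but the table states neither.

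The sufficiency sentence is also soft: it refers to some outcomes and gives examples, and it rests on pilot rates that are themselves imprecise. Still, proximal colon ADR is one of the three examples named.

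Finally, the SAP's secondary analysis compares groups by chi-square and adjusts for gender in a model, which can be read as a test in both sexes together. On that reading a WE rate of 20% does far less harm (step 4). The protocol's secondary hypothesis, however, is worded for both male and female Veterans, and the sufficiency statement is made for men alone, so the male figure still needs to be right.

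A reader might infer that the trial is underpowered for male proximal colon ADR, or that 76 was miscalculated. The documents support neither. Nothing identifies 17% as the wrong entry, and 76 follows exactly from 17% and 40%.

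**Conclusion.** The concern holds as an inconsistency between inputs. WE rates of 17% proximal and 20% right colon cannot both describe the same 87 men under the protocol's definitions. At least one entry is wrong, or a row rests on a denominator or segment definition that is not given.

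The consequence is limited to one secondary claim and depends on which entry fails. With WECAC at 40%, 80 men per group give about 91% power if WE is 17%, and at most about 80% if WE is 20% or more. This assumes a two-sided 5% test, 1:1 allocation, and a male-only comparison at the recruited number. The severity is minor.

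**What to change.** Check the proximal and right colon rows of the male table against the pilot counts. Show count and denominator for each, as the protocol's Table 6 does for its combined ADRs, and state the segment definition if the pilot used a different one. Then:

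- If WE proximal ADR is 17%, correct or explain the right colon row only, and keep 76 per group and the sufficiency claim.
- If WE proximal ADR is 20% or more with WECAC at 40%, stop calling 160 men sufficient for proximal colon ADR. State the recomputed figure instead: at least 106 per group for 90% power, and at most about 80% power at 80 per group.
- If the counts give any other pair of rates, recompute the row with the same formula and word the claim to match.

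The cost is one look at the pilot data, one or two table rows, and at most one sentence. Enrolment, the primary sample size, the analysis and the status of the endpoints stay as they are.
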